9.4.3 ANALYSIS OF THE SECONDARY EFFICACY ENDPOINT(S)

The secondary efficacy analysis will be performed on all Subjects in FAS Population (Efficacy Evaluable Population) and PP Population comparing Group 1 (Galnobax® plus SoC) and Group 2 (SoC only) only and are defined as:

- Time to Target Ulcer Closure in days = (Date of Target Ulcer Closure by Week 12 of treatment or earlier – Date of first dose of Study treatment) + 1
- Proportion of Subjects achieving Target Ulcer Closure till End of Study = [Number of Subjects having Target Ulcer Closure at by week 24 or earlier /Total number of Subjects in the Population].

For analysis of secondary endpoint of time to Target Ulcer closure during the 12-week Treatment Phase, Cox proportional hazards model with treatment group, ulcer type (plantar or non-plantar) and site as independent factors and baseline ulcer size as continuous covariate will be used to compare between the treatment groups. In addition, Kaplan-Meier analysis will also be used to depict the median time (days) to Target Ulcer closure for the two treatment groups.

The other categorical secondary endpoints comparing proportion of Target Ulcer using different criteria will be analyzed using chi-square/fishers exact test as well as the same method described for primary efficacy analysis with the same model of logistic regression.

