10.4	Protocol Amendment History	56
11	APPENDICES.....	57
12	REFERENCES	64

List of Tables

Table 1 Subject progression as per condition of Target Ulcer.....	17
Table 2 Dosing schedule	18
Table 3 Composition of Galnobax®	22
Table 4 Labelling information of Galnobax®	25
Table 5 Assessment of Intensity	38
Table 6 List of Abbreviations.....	54

Definitions

Term	Definition
Diabetic Foot Ulcer (DFU)	Diabetic foot ulceration is full-thickness penetration of the dermis of the foot in a person with diabetes.
Standard of Care (SoC)	Wound cleaning by normal saline, maintenance of moist wound environment and off-loading of the Target Ulcer. In addition, during Site Visits removal of necrotic, infected and/or nonviable tissue by debridement and management of infection to be done by the Investigator, if required.
Target Ulcer Closure	100% re-epithelialization without drainage or dressing requirement (except if recommended by the Investigator for covering of the closed wound) to be confirmed by two consecutive site visits two weeks apart from first observation of closure.
Time to Target Ulcer Closure	Duration of first observation of closure from Baseline visit for those Target Ulcers for which conditions for Target Ulcer Closure were satisfied.
Intent to Treat (ITT) Population (Safety Evaluable Population)	All Subjects who are randomized and received at least one dose of Study medication will be included in ITT Population.
Full Analysis Set (FAS) Population (Efficacy Evaluable Population)	All randomized Subjects who had at least 6 weekly Site Visits for the assessments of Target Ulcer Closure or had Target Ulcer closed earlier than 6 weeks.
Per Protocol (PP) Population	All randomized Subjects who have completed the Study without any major protocol deviation.

STATEMENT OF COMPLIANCE

The trial will be conducted in accordance with International Council for Harmonization Good Clinical Practice (ICH GCP), Declaration of Helsinki and GCP guidelines as per Central Drugs Standard Control Organization (CDSCO), Directorate General of Health Services (DGHS), Government of India. The Principal Investigator will ensure that no deviation from, or changes to the protocol will take place without prior agreement from the Sponsor and documented approval from the Ethics Committee (EC), except where necessary to eliminate an immediate hazard(s) to the trial participants. All personnel involved in the conduct of this Study have completed Human Subjects Protection and ICH GCP Training.

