^j Subject Education and training on Diabetes management and use of off-loading device will be done as and when required

^k The AE reporting will begin from the application of the first dose of the IP from the Baseline Visit

^l Debridement of ulcer as and when necessary during site visit

^m Nutritional information should be provided to Subject as and when necessary

ⁿ Photographs of both the legs will be taken from various angles to ensure that there are no more than three ulcers on both the legs

^o In case the ulcer/wound closes within 12-weeks of Treatment Phase, the Subject will immediately enter the 12-weeks of Follow-Up Phase. In case of the Subject, whose Target Ulcer reopens during 12-weeks of Treatment Phase (within 84 days from Baseline) which is prior to the confirmation of Target Ulcer closure, the Subject would be given the treatment to complete 12-week of Treatment Phase

^p During Follow-Up Phase, if the Target Ulcer has reopened after confirmation of its closure, the Subject will still be continued with the Follow-up assessment.

^q This window period is from the Screening Visit

^r EOT is at week 12 visit or any visit on which first observation of Target Ulcer closure has happened or treatment is Stopped

^s EOS is at week 24 visit or any visit on which the Subject exits the Study

^t Window period of ±3 days will be allowed for each Treatment visit as well as FU1 and FU2 visits and window period of ±5 will be allowed for FU3 and FU4

Note: *Dispensing of Wound dressing material will be provided as long as required

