3 OBJECTIVES AND ENDPOINTS

OBJECTIVES	ENDPOINTS	JUSTIFICATION FOR ENDPOINTS
Primary		

 To assess the efficacy of Galnobax® in terms of proportion of Subjects achieving Target Ulcer Closure within 12-week Treatment Phase upon application of Galnobax® plus Standard of Care as against only Standard of Care treatment, as assessed by the blinded Investigator 	
The efficacy assessment will involve Galnobax® plus Standard of Care and only Standard of Care groups
 
Efficacy endpoints:
 
Proportion of subjects achieving Target Ulcer Closure within 12-week Treatment Phase, as assessed by blinded Investigator
	Complete wound closure of a chronic, nonhealing wound is one of the most important objective and clinically meaningful wound healing endpoint
Secondary		
Efficacy	Efficacy endpoints	

 To compare Time to Target Ulcer Closure within the 12-week Treatment Phase, upon application of Galnobax® plus Standard of Care as against only Standard of Care treatment, as assessed by the blinded Investigator 	
 Time to Target Ulcer Closure during the 12-week Treatment Phase, as assessed by the blinded Investigator 	This endpoint evaluates clinically meaningful reduction in the time to Target Ulcer Closure using a time-to-event analysis (the event being first observation of complete closure)

 To compare proportion of Subjects achieving Target Ulcer Closure till End of Study upon application of Galnobax® plus Standard of Care as against only Standard of Care treatment, as assessed by the blinded Investigator 	
 Proportion of Subjects achieving Target Ulcer Closure till End of Study, as assessed by the blinded Investigator 	This endpoint is for evaluating sustained effect of the treatment post its discontinuation
Safety		

 To investigate the safety of Galnobax® treatment during the Study 	
 Proportion of Subjects with treatment emergent adverse events (TEAEs) 	This endpoint evaluates safety of Galnobax® by assessing TEAEs

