- Assessment of local pain in terms of 11-point (0-10) universal pain scale for the Target Ulcer (See *Attachment 4*)
- Assessment of local edema in terms of 5-point (0-4) edema scale for the Target Ulcer (See *Attachment 4*)
- Assessment of local erythema in terms of 5-point (0-4) erythema scale for the Target Ulcer (See *Attachment 4*)
- Clinical assessment of infection status of non-Study ulcer(s)
- Subject education on diabetes management and off-loading as and when required
- Recording of concomitant medications
- AE recording
- Nutritional information (i.e., the importance of diet in controlling glucose levels) will be provided to and reviewed. Further counseling to the Subject will be available on request during the course of Study
- Study Diary review will be done by unblinded Investigator for treatment compliance check and use of offloading device at each visit of the Study Nurse to the investigator Site

Follow-up Visit Week 14 to Week 24 (FU1 to FU4) [V15/Day 98 to V18/Day 168 (Window period $\pm 3/\pm 5$ days)]

The Subjects whose Target Ulcer is closed (first observation of Target Ulcer Closure) or the Subject who completes the 12-weeks of Treatment Phase, whichever is earlier, will immediately enter the Follow-Up (FU) Phase of 12-weeks. All Subjects who enter the Follow-Up Phase are required to attend the Follow-up visit FU1-two weeks after EOT; FU2-four weeks after EOT, FU3-eight weeks after EOT and FU4-twelve weeks after EOT, regardless of whether the Target Ulcer is open/closed/re-opened.

For the Subjects whose Target Ulcer has closed within the 12-week Treatment Phase, the 12-week Follow-Up Phase is divided into 4-week Closure Confirmation period and 8-week Observation period. The Closure Confirmation period will be of total four weeks with two visits two weeks apart for confirming initial closure of the Target Ulcer. The Observation period will be of total eight weeks with two visits, four weeks apart for assessing quality of healing, progress of ulcer closure and AEs, if observed.

For the Subjects whose Target Ulcer has not closed within 12-week Treatment Phase, the 12-week Follow-Up Phase will be considered as 12-week Observation period.

Subjects who have entered the Follow-Up Phase will be subjected to SoC treatment as deemed necessary by the Investigator. Unless recommended by the Investigator otherwise, SoC during the Follow-Up Phase will be self-administered by the Subject.

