The Subject whose Target Ulcer has closed within 12-week Treatment Phase and has entered the Follow-Up Phase will continue to use protective covering or bandage (if advised by the Investigator) on the Target Ulcer until confirmation of the Target Ulcer closure. If the Target Ulcer remains closed during Closure Confirmation period, then the Target Ulcer will be confirmed to be closed. The time to Target Ulcer closure will be the time from the Baseline Visit when Target Ulcer was first observed closed for which Target Ulcer Closure was confirmed.

During this follow-up phase, if the Target Ulcer reopens during the Closure Confirmation period which lies within 84 ± 3 days from Baseline visit, the Subject would be given the treatment to complete 12-week of Treatment Phase. For example, if the Target Ulcer closes before 8 weeks of treatment and reopens within 4 weeks of Closure Confirmation period, the Subject will restart the treatment and continue only till 12-weeks (84 ± 3 days) of treatment from Baseline visit. On completion of that period, Subject will enter the Follow-Up Phase.

During this follow-up phase, if the Target Ulcer reopens after confirmation of the Target Ulcer closure, the Subject will still be continued with the Follow-up assessment period and further evaluations would be as per Follow-up visit scheduled.

During this 12-week Follow-Up phase (84 ± 5 days from EOT), the closed Target Ulcer will be monitored to distinguish actual healing from transient wound coverage and for AEs, if any.

All Subjects will undergo following assessments during FU1 to FU4 visits

- Sample collection for Urine pregnancy test (as necessary) at FU2
- Vital signs (blood pressure, pulse rate, respiratory rate, and temperature)
- Systematic physical examination and body weight at EOS or FU4, whichever is earlier
- Laboratory tests (hematology tests, biochemistry, and HbA1c) at EOS or FU4, whichever is earlier
- Measurement of random blood glucose. If abnormality is observed, the Investigator may recommend pre- and post-prandial blood glucose measurement and modify dose or medication for adequate blood sugar control
- ECG or 2 D echocardiography (2D-ECHO only if ECG is not conclusive) at FU1
- Subject Diary review will be done by blinded Investigator for all subjects in follow up Phase
- Offloading, dressing compliance

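### The secondary endpoint meant to show sustained effect most naturally counts ulcers ever confirmed closed, and its confirmation rule does not match the follow-up visits for closures first seen after treatment

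*Combined protocol and SAP*

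**What the plan says.** **Purpose.** The justification column in section 3 says of the proportion with closure till End of Study: "This endpoint is for evaluating sustained effect of the treatment post its discontinuation". Sections 4.2 and 8 also name the strength of the closed ulcer, and telling true healing from temporary coverage, among the reasons for the 12-week follow-up.

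**Formula.** Section 9.4.3 defines the numerator as "Number of Subjects having Target Ulcer Closure at by week 24 or earlier", divided by all subjects in the analysis population.

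**Closure.** The Definitions table requires full re-epithelialization "to be confirmed by two consecutive site visits two weeks apart from first observation of closure".

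**Visits.** Follow-up runs from EOT: FU1 and FU2 at two and four weeks, then "FU3-eight weeks after EOT and FU4-twelve weeks after EOT". Footnote r of the schedule in section 1.3 states: "EOT is at week 12 visit or any visit on which first observation of Target Ulcer closure has happened or treatment is Stopped". Footnote s states: "EOS is at week 24 visit or any visit on which the Subject exits the Study".

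**Reopening.** Section 8 gives only a conduct rule: "if the Target Ulcer reopens after confirmation of the Target Ulcer closure, the Subject will still be continued with the Follow-up assessment period". Nothing says whether that subject still counts as a success.

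**Ulcers open at week 12.** Section 8 states: "For the Subjects whose Target Ulcer has not closed within 12-week Treatment Phase, the 12-week Follow-Up Phase will be considered as 12-week Observation period". The Closure Confirmation period is described only for ulcers that closed within the Treatment Phase.

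**The concern.** There are two gaps between what the endpoint is for and what it counts.

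First, a count of ulcers ever confirmed closed cannot show loss of effect. Reopening before FU2 prevents confirmation of that closure, but reopening after FU2 changes nothing. The secondary proportion can never fall below the primary proportion in the same population. Follow-up data on weeks 4 to 12 after EOT would be collected partly to judge durability and then enter no efficacy comparison. Late reopening could appear in the per-visit listings (section 9.4.12) or as an adverse event (section 8.2.5, subject to the exclusion of disease progression and lack of efficacy in 8.2.7), but section 9.4.4 plans no formal analysis of safety data.

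Second, an endpoint that runs past week 12 should add closures first seen in follow-up. The confirmation rule does not fit the visits at which those closures would be seen, and the text does not say what to do instead. Two analysts could obtain different proportions from the same data.

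**Working it through.** **Plan's own figure.** The plan states no figure for this endpoint. The planning rates in section 9.2 are 39% (SoC) and 60% (Galnobax), with 120 evaluable subjects per group. A two-sided 5% pooled two-proportion calculation at 90% power gives 118 per group, and 120 gives power of 0.907. The plan's sample size is reproduced, and nothing below alters it.

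**Reopening: when is status last seen?** FU4 falls at EOT + 12 weeks, and EOT is the visit of first closure.

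| First closed (week) | Confirmed at FU2 (week) | FU4 (week) |
|---|---|---|
| 4 | 8 | 16 |
| 8 | 12 | 20 |
| 12 | 16 | 24 |

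Only ulcers closing at week 12 reach week 24 in the study. For earlier closers, the week 24 of the formula and the End of Study of the endpoint's name are different times.

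**Late closures: does the rule fit?** The strict rule needs closed status 2 and 4 weeks after first closure. For an ulcer open at week 12, the nominal visits are at weeks 14, 16, 20 and 24.

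| First closed at | Later visits (weeks after) | Strict rule | One later visit 2 weeks on | Any two later visits | Any one later visit |
|---|---|---|---|---|---|
| FU1 (14) | +2, +6, +10 | no | yes | yes | yes |
| FU2 (16) | +4, +8 | no | no | yes | yes |
| FU3 (20) | +4 | no | no | no | yes |
| FU4 (24) | none | no | no | no | no |

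**Do the visit windows help?** In days after EOT the visits are FU1 14±3, FU2 28±3, FU3 56±5 and FU4 84±5. The possible gaps are:
- FU1 to FU2: 25 − 17 = 8 to 31 − 11 = 20
- FU2 to FU3: 51 − 31 = 20 to 61 − 25 = 36
- FU3 to FU4: 79 − 61 = 18 to 89 − 51 = 38

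A closure first seen at FU1 fits two gaps of 14±6 days only if FU2 falls on its last permitted day (31) and FU3 on its first (51). A closure first seen at FU2 needs a tolerance of 10 days: day 31 to day 79 is 48 days, at best two gaps of 24. FU3 and FU4 lack two later visits.

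**Size of reopening.** Section 2.1 cites recurrence above 50% over 2 to 5 years. At constant hazard, the 8-week risk is 1 − 0.5^(8 weeks / span): 5.2% for 2 years and 2.1% for 5 years, rounded below to 5% and 2%. Planned closures are 0.39 × 120 = 46.8 (SoC) and 0.60 × 120 = 72 (Galnobax).

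| Reopening, SoC / Galnobax | Still closed, SoC | Still closed, Galnobax | Difference (points) |
|---|---|---|---|
| 0 / 0 | 39.0% | 60.0% | 21.0 |
| 2% / 2% | 38.22% | 58.8% | 20.6 |
| 5% / 5% | 37.05% | 57.0% | 19.95 |
| 2% / 5% | 38.22% | 57.0% | 18.8 |
| 5% / 2% | 37.05% | 58.8% | 21.75 |

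That is 0.9 to 2.3 SoC subjects and 1.4 to 3.6 Galnobax subjects.

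**Size of late closure.** The documents give no rate. Assume a share L of ulcers open at week 12 closes in follow-up, equal in both arms. Open ulcers number 0.61 × 120 = 73.2 and 0.40 × 120 = 48. If all late closures count:

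| L | Extra SoC | Extra Galnobax | SoC | Galnobax | Difference (points) |
|---|---|---|---|---|---|
| 10% | 7.3 | 4.8 | 45.1% | 64.0% | 18.9 |
| 20% | 14.6 | 9.6 | 51.2% | 68.0% | 16.8 |
| 30% | 22.0 | 14.4 | 57.3% | 72.0% | 14.7 |

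If none count, the result stays at 39% against 60%, the primary result.

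**The case against.** The strongest reply is that the text is ambiguous, not wrong. The numerator is garbled, and End of Study is specific to each subject, so the endpoint could mean status at that subject's own last visit. A reader might infer that such a reading fails because early closers never reach week 24. The documents do not support that inference: early closers attend FU4, and the ulcer is photographed there even if closed. The status reading is workable, but the text does not choose it, and the words after the garble point to a cumulative count.

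Sustained effect might also mean further closures after treatment stops. That is a fair reading, but a cumulative count mixes those closures with every on-treatment closure, and they are the ones the confirmation rule does not fit.

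A reader might infer that no closure first seen in follow-up can ever be confirmed. That is too absolute. The FU1 and FU2 windows already accept a gap of 8 to 20 days for on-treatment closers, and at that tolerance a closure first seen at FU1 can just qualify. Section 8 also provides for unscheduled visits to record closure, though it does not adapt them to a subject already in follow-up.

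Section 9.4.1 leaves detailed methods to a separate SAP, which is not among the documents. It may settle both points. But the formula already stands in the protocol, and nothing there says it will be redefined.

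The objection that the numbers are small stands. The recurrence figure concerns any foot ulcer over years, not reopening of a confirmed Target Ulcer, and the late-closure rates are assumptions.

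**Conclusion.** The point holds as a mismatch between stated purpose and formula on one secondary endpoint. On the natural reading the measure cannot show loss of effect after FU2. Under the strict confirmation rule it adds almost nothing to the primary.

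The numerical effect may be small. Equal reopening of 2% to 5% lowers a 21-point difference by about 0.4 to 1.05 points, and unequal reopening within that range gives 18.8 to 21.75. The choice of rule for late closures could matter more: 18.9 to 14.7 points if 10% to 30% close late in both arms and all are counted. These figures rest on the planning rates, a constant-hazard conversion of a recurrence figure stated only as more than 50%, and assumed late-closure rates and splits by arm.

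A reader might infer that the efficacy conclusion is threatened, or that the treatment difference is materially inflated. The documents support neither: the primary endpoint and the 120 per group are unaffected, and a large effect would need high or unequal reopening rates that the documents do not give. The change is worth making because it is cheap and uses data already planned.

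**What to change.** In section 9.4.3, keep the cumulative endpoint, but do not describe it as sustained effect in section 3. Then:

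1. **Add a supportive sustained-closure analysis** in the same population with the same logistic model. Success is closure first observed in the Treatment Phase, confirmed at FU1 and FU2, and still present at FU4 (12 weeks after EOT) with no recorded reopening. Name FU4 rather than week 24 or End of Study. Count a missing FU4 as not sustained, with a sensitivity analysis using last observed status, so that dropout and durability can be told apart.
2. **Report reopening among confirmed closures by arm.**
3. **State an analysis rule for closures first seen in follow-up** that uses existing visits. For example, a closure first seen at FU1 or FU2 counts in the cumulative endpoint if the ulcer is closed at the next two scheduled visits. Closures first seen at FU3 or FU4 are reported separately as unconfirmed.
4. **Tidy the numerator** so that it says plainly that it is cumulative, and carry the wording to the synopsis, section 9.1 and the SAP.

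The cost is a little more analysis and a wording amendment, which needs ethics committee approval (Statement of Compliance) across about 40 sites. No new visits or data are needed. The sustained rate may come out lower than the primary rate, and missing FU4 visits will count against an arm in the main version.

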9 STATISTICAL CONSIDERATIONS

9.1 STATISTICAL HYPOTHESES

Primary Efficacy Endpoint(s):

Proportion of Subjects achieving Target Ulcer closure within 12-week Treatment Phase, as assessed by blinded Investigator.

Secondary Efficacy Endpoint(s):

- Time to Target Ulcer Closure during the 12-week Treatment Phase, as assessed by the blinded Investigator
- Proportion of Subjects achieving Target Ulcer Closure till End of study, as assessed by the blinded Investigator

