9.2 SAMPLE SIZE DETERMINATION

This Study will have FAS Population (Efficacy Evaluable Population) of minimum of 240 Subjects (minimum of 120 each in Group 1 and Group 2). To ensure this and assuming 20% drop out rate, the population of two groups would be up to 300 Subjects. For safety analysis of Vehicle of Galnobax®, maximum of 50 Subjects will be recruited in Vehicle plus SoC group. Thus, overall population of maximum of 350 Subjects will be recruited in the Study.

Sample Size Determination and Rationale:

The sample size calculation has two components. One is based on statistical power and the other is based on clinical judgment.

The sample size calculation is based on the primary endpoint for the Study that is proportion of Subjects achieving complete closure of Target Ulcer within 12-week Treatment Phase, as determined by blinded Investigator's assessment.

The sample size is obtained based on the assumption that there will be a clinically meaningful difference of 21%, (i.e., 39% of SoC vs 60% of Galnobax®-treated achieved complete closure of Target Ulcer, odds ratio of 0.65). This assumption is based on the following:

- a. Literature reports from various DFU trials showed that average percent wounds closed using SoC treatment is 24% globally.^{5 27} However, percent wounds closed using SoC treatment in recently completed DFU trial in India is reported to be 37.8%.²⁸ In view of this, it is assumed that 39% wounds may close in the SoC group.
- b. In Phase 1/2 study of Galnobax®, 60% wounds closed within 12-week of Galnobax® treatment. Furthermore, 67% wounds were closed in Galnobax® arm for wounds with wound age > 6 weeks. In view of this, the inclusion criterion is revised to include Subjects with wounds of at least 6 weeks (which was 4 weeks in Phase 1/2 study) and it is assumed that 60% wounds may close in the Galnobax® treatment group.

To meet the Type I error rate of 0.05 (95% confidence interval), 2-sided analysis and 90% power, 120 Efficacy Evaluable Subjects in Group 1 and Group 2 will be required for making the FAS Population in the Study as 240. To accommodate the potential drop outs rate of 20%, a total of 300 Subjects will be randomized in these Groups to ensure more than 90% power for the primary endpoint analysis (i.e., proportion of Subjects achieving Target Ulcer Closure within 12-week Treatment Phase).

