The safety evaluation of Vehicle of Galnobax® will be done by recruiting population of 50 Subjects in the Vehicle plus SoC group. As there is not hypothesis testing or statistical comparison proposed for this arm, this population might not be statistically significant, but would enough to give reasonable estimate of safety for Vehicle of Galnobax®.

9.2.1 RANDOMIZATION AND STRATIFICATION OF STUDY POPULATION:

Prior to randomization, Subjects will be stratified by location of Target Ulcer (planter or non-planter), and the Target Ulcer size ($<5\text{ cm}^2$ or $\geq 5\text{ cm}^2$). The randomization will be done at the ratio of 3:3:1 in one of the following groups, using an IWRS:

- Galnobax® 14% plus SoC or
- SoC or
- Vehicle plus SoC

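### Closure till End of Study has two tests with neither decisive, and the two secondary endpoints have no testing order, so the chance of at least one false-positive secondary result exceeds 5%

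*Combined protocol and SAP*

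**What the plan says.** Section 9.4.3 covers two secondary efficacy endpoints.

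- **Time to closure within 12 weeks** has one comparative method: a Cox model with treatment, ulcer type, site and continuous ulcer size. Kaplan-Meier is added only to show median times.
- **Closure till End of Study** is the only categorical secondary endpoint listed, so the sentence on categorical endpoints must apply to it. The method is "chi-square/fishers exact test as well as the same method described for primary efficacy analysis". The primary method (9.4.2) is a logistic model with treatment, ulcer type, site and continuous ulcer size.

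Both endpoints are analysed in the FAS and the PP population. Section 4.2 leans towards the FAS, but 9.4.3 does not rank the two.

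On randomisation, 9.2.1 says "Subjects will be stratified by location of Target Ulcer", and by ulcer size with a cut at 5 cm².

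The only significance level is in 9.2: "To meet the Type I error rate of 0.05 (95% confidence interval), 2-sided analysis and 90% power". That section ties it to one endpoint: "The sample size calculation is based on the primary endpoint for the Study". No level, order, alpha split or adjustment is given for the secondary endpoints. Section 9.4.1 says that a separate SAP, issued before database lock, will detail the analyses outlined in the protocol.

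**The concern.** The two methods for closure till End of Study test the same hypothesis in different ways. Chi-square/Fisher ignores the location and size strata; the logistic model adjusts for location, size and site. They can fall on opposite sides of 0.05, and the plan does not say which result stands. The slash leaves open even which unadjusted test is meant. Time to closure is compared alongside with no sequence.

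Section 3 presents these endpoints as evidence of faster healing and of an effect that lasts after treatment stops. If either is claimed from a Phase 3 trial, the reader needs to know which p-value was decisive and how often such a claim would arise by chance.

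**Working it through.** **1. The plan's own figure.** Inputs from 9.2: 39% versus 60%, two-sided 0.05, 90% power. With the pooled formula and mean rate 0.495:

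n = [1.960·√(2·0.495·0.505) + 1.2816·√(0.39·0.61 + 0.60·0.40)]² / 0.21² = (1.386 + 0.886)² / 0.0441 ≈ 117.0, so 118 per group.

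The plan states 120, which gives 90.7% power; 240/0.8 = 300 randomised. The primary calculation is reproduced, and nothing below changes it.

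**2. Two endpoints, one test each, each at exactly 5%.** The probability that at least one is falsely significant depends on the correlation ρ of the test statistics, which the documents do not give. At ρ = 0 it is 1 − 0.95² = 9.75%. From the bivariate normal:

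| ρ | 0 | 0.5 | 0.7 | 0.8 | 0.9 | 1 |
|---|---|---|---|---|---|---|
| At least one | 9.75% | 9.1% | 8.35% | 7.8% | 7.0% | 5% |

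**3. The planned tests under no treatment effect.** Simulation with 4,000 trials per scenario and 240 subjects (300 in one scenario). Assumptions not in the documents: closure 39-50% by week 12 and 50-63% by week 24 in both arms, half the ulcers plantar, weak to moderate effects of location, size and site, and subjects spread at random over sites. Arms were balanced overall but not within strata. Monte Carlo error is about 0.3-0.6 points. Entries are the percentage of trials with p < 0.05, as ranges over scenarios.

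| | No site effects or terms (3 scenarios) | 20 sites (1) | 40 sites (5) |
|---|---|---|---|
| Chi-square alone | 4.6-4.9 | 4.7 | 4.7-5.8 |
| Fisher alone | 3.4-3.7 | 3.6 | 3.3-4.5 |
| Logistic alone | 5.0-5.3 | 5.5 | 6.8-7.2 |
| Cox alone | 4.3-4.8 | 5.3 | 6.3-7.2 |
| Chi-square or logistic | 5.7-6.6 | 7.8 | 8.5-9.7 |
| Fisher or logistic | 5.4-5.8 | 7.1 | 7.7-9.0 |
| Cox or chi-square | 7.6-8.4 | 8.8 | 9.6-11.5 |
| Cox or logistic | 8.0-8.4 | 9.0 | 10.3-12.7 |
| Cox, chi-square or logistic | 8.4-9.9 | 11.1 | 11.9-14.6 |

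The plan has about 40 sites (4.1), or 240/40 = 6 evaluable subjects per site on average.

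**4. Separating the two sources.** In the base 40-site scenario the logistic model alone rejects 6.8%. That is 1.8 points above 5% with no second test involved, and it comes from the many site terms. Allowing chi-square as well raises it to 9.05%, so the second method adds 9.05 − 6.82 = 2.2 points. In the matching scenario without site it adds 6.20 − 5.18 = 1.0 point.

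**5. The remedy's tests.** A separate null simulation with 40 sites gave chi-square 4.5%, Cochran-Mantel-Haenszel stratified by location and size 4.9%, logistic with site 6.5%, and chi-square or logistic 8.1%. The stratified test holds its level; the 40-site logistic model does not.

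**The case against.** The strongest case against is this. The primary endpoint has one named model. No section calls the secondary endpoints key or confirmatory, or attaches a success criterion to them. Listing two analyses is not a rule that either one suffices. A separate SAP, not among the documents, is to give the detailed methods. The unadjusted test is also valid: chi-square rejects 4.6-5.8% under the null and Fisher less, so ignoring the strata mainly costs power.

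Most of this stands, and it limits the point. The deferral does not remove it. Section 9.4.1 promises detail for the analyses as outlined, and the outline itself prescribes both tests. Sections 9.4.7 and 9.4.8 expressly send missing data and outliers to the SAP; nothing does so for the lead test or for multiplicity. A SAP that follows 9.4.3 faithfully would carry both tests forward.

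A reader might infer that each secondary test is really run at about 8% in place of a stated 5%. The documents do not support that. No level is stated for any secondary test; the 0.05 belongs to the primary sample size. Multiplicity raises the chance of at least one false positive, not the level of each test. No single test in the simulations reaches 8%: the range is 3.3% to 7.2%. Nor does the two-method point extend to time to closure, where Cox is the only test.

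**Conclusion.** The point holds as a gap in the secondary analysis: two methods for one hypothesis with no lead, and two endpoints with no order. The resulting chance of a false-positive secondary finding is above 5%. It is about 6-10% for either method on closure till End of Study, 5-9.75% for the two endpoints if each test holds exactly 5%, and about 8-15% across all three planned tests. These figures rest on assumed closure rates, site effects and correlations. The upper ends reflect the 40 site terms as well as multiplicity. Running everything in both FAS and PP adds further p-values that these figures do not count.

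The primary endpoint and the sample size are untouched. This is a cheap improvement, not a threat to the main conclusion.

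**What to change.** In 9.4.3, carried into the SAP before database lock:

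1. Name one decisive test for closure till End of Study, in the FAS. Preferred: a Cochran-Mantel-Haenszel test stratified by location (plantar or non-plantar) and size (<5 or ≥5 cm²). Alternative: the logistic model with treatment, location and size, without 40 site terms. Label the other methods and the PP analysis as supportive.
2. Test in fixed order at two-sided 0.05: primary endpoint, then time to closure, then closure till End of Study. Stop formal claims at the first non-significant result.
3. Take the 40 site terms out of the Cox model too. A fixed order holds 5% only if each test in it does. Keeping the site-adjusted logistic model as the single test would leave its level at about 6.5-7.2%. The primary model in 9.4.2 also includes site; its level is a separate question and was not computed here.

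The cost is wording only: no extra subjects and no alpha taken from the primary endpoint. The downside is that a later secondary endpoint cannot be formally claimed if an earlier one fails. Leaving site out may also lose some precision if closure differs much between sites.
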